9.3 Procedures at each visit

9.3.1 Split into subtitles by type of visit

Visit 1, Screening (Day -1 or day 0):

Informed consent will be obtained before any study-specific tests or evaluations will be performed.

- Patients who are admitted to the medical ward with confirmed or suspected SARS-CoV-2 infection will be screened within 72 hours after admission on the ward. Screening will be based on routinely available data and laboratory tests with only the pregnancy test as study-specific intervention/test if necessary before screening of the patients. Results from prior tests that will be used for screening potentially eligible subjects will be recorded in the eCRF.
- Selection of potential participants according to inclusion and exclusion criteria.
- Explanation of patient information including study purpose and signature of informed consent form.
- Study enrolment
- Assignment of the trial subject identification number
- Pregnancy test if applicable.
- Eligibility check (in- and exclusion criteria)
- Randomisation, which can either occur on the same day of hospital admission or within 72 hours after hospital admission.

Visit 2, Intervention period (Day 0)

- Assessment of demographics, medical history and concomitant medication
- Assessment of vital signs including respiratory rate.
- Assessment of WHO ordinal scale and need for oxygen supplementation
- Collection of blood (12ml) for analysis of ferritin, IL-6, D-Dimer, C1INH concentration, and in Basel (optional for other centers): collection of blood (5ml) and urine (5ml) for the analysis of complement proteins, parameters of the contact activation and coagulation system, renal injury markers, and inflammatory cytokines. Routine full blood count, coagulation and biochemistry studies will only be performed if results from prior tests on the same day are not available.
- Assessment of reference serum creatinine
- Virology testing (quantitative SARS-CoV-2 PCR) on a nasopharyngeal sample if not already performed before inclusion into the study. This is optional for other centers except Basel.
- Following randomisation, participants in the active treatment group will receive 8400 U of conestat alfa as slow intravenous injection. The time of dosing and the dose will be recorded. Subsequently, 4200 U will be administered every 8 hours in the active trial group.
- AEs occurring after the administration will be recorded.
- Only in Basel and in the active treatment group: Collection of blood (5ml) for the analysis of C1INH levels and activity 10 (+/-5 minutes) after the first administration.

Visit 3, Intervention period (Day 1)

- Administration of 4200 U of conestat alfa every 8 hours in the active treatment group as per treatment schedule. The time of dosing and the dose will be recorded.
- Assessment of vital signs including respiratory rate.
- Assessment of WHO ordinal scale and need for oxygen supplementation
- Documentation of ICU admission and/or non-invasive or invasive ventilation
- Collection of blood (12ml) for analysis of ferritin, D-Dimer, C1INH concentration, and in Basel (optional for other centers): collection of blood (5ml) and urine (5ml) for the analysis of complement proteins, parameters of the contact activation and coagulation system, renal injury markers and inflammatory cytokines. Routine full blood count, coagulation and biochemistry studies will only be performed if results from prior tests on the same day are not available.
- Only in Basel and in the active treatment group: Collection of blood (5ml) for analysis of C1INH levels and activity 10 (+/-5 minutes) after any of the three administrations of conestat alfa on that day.

- Assessment of AEs.

Visit 4, Intervention period (Day 2)

- Administration of 4200 U of conestat alfa every 8 hours in the active treatment group as per treatment schedule. The time of dosing and the dose will be recorded.
- Assessment of vital signs including respiratory rate.
- Assessment of WHO ordinal scale and need for oxygen supplementation
- Documentation of ICU admission and/or non-invasive or invasive ventilation
- Assessment of AEs.

Visit 5, Intervention period (Day 3-13 during hospital admission)

- Completion of treatment with conestat alfa (9 administrations in total including the first 8400 U administration) in the active treatment group as per treatment schedule. The time of dosing and the dose will be recorded.
- Assessment of vital signs including respiratory rate.
- Assessment of WHO ordinal scale and need for oxygen supplementation. If the patient was already discharged before day 7, the assessment of the WHO ordinal scale will be conducted via a short telephone interview (Score 1 or 2).
- Documentation of ICU admission and/or non-invasive or invasive ventilation
- Routine laboratory tests will be performed on days 3, 5, 7 and 10 during admission according to standard procedures, and should include a set of hematology, coagulation and biochemistry parameters. Additionally, blood (5ml) for analysis of ferritin, IL-6, D-Dimer, C1INH concentration will be collected at the same time point, and in Basel (optional for other centers): collection of blood (5ml) and urine (5ml) for the analysis of complement proteins, parameters of the contact activation and coagulation system, renal injury markers and inflammatory cytokines.
- Virological assessment (quantitative SARS-CoV-2 PCR in respiratory specimen) should be performed on day 4-7 (according to local standard). This is optional for all centers except Basel.
- Assessment of AEs

Visit 6, Follow-up (Day 14 (+/-2 days) or at discharge)

- Physical examination including body weight.
- Assessment of vital signs including respiratory rate.
- Assessment of WHO ordinal scale and need for oxygen supplementation
- Documentation of ICU admission and/or non-invasive or invasive ventilation
- Laboratory assessment including routine hematology, coagulation and biochemistry studies (7ml). Routine laboratory tests will be performed every second day during admission according to standard procedures. Additional sample collection will be required in patients without routine testing on the day of discharge. Additionally, blood (5ml) for analysis of ferritin, IL-6, D-Dimer, C1INH concentration will be collected at the same time point, and in Basel (optional for other centers): collection of blood (5ml) and urine (5ml) for the analysis of complement proteins, renal injury markers and inflammatory cytokines.
- Virological assessment (quantitative SARS-CoV-2 PCR in respiratory specimen) will be performed on day 14 (when still admitted) or at discharge if on day 10-13. This is optional for all centers except Basel.
- Assessment of AEs.

Visit 7, Follow-up (week 4 +/- 5 days, telephone interview or study visit if still admitted)

- Assessment of adverse events, WHO ordinal scale, admission to ICU and/or mechanical ventilation by structured telephone interview. If necessary, medical charts will be reviewed, discharge summaries will be obtained or the patients' general practitioner will be contacted regarding specific follow-up information.

10. SAFETY

10.1 Drug studies

The Sponsor's SOPs provide more detail on safety reporting.

During the entire duration of the study, all adverse events (AE) and all serious adverse events (SAEs) are collected, fully investigated and documented in source documents and electronic case report forms (eCRF). Study duration encompassed the time from when the participant signs the informed consent until the last protocol-specific procedure has been completed, including a safety follow-up period.

As the frequency of comorbidities in the patient population under study is significant and clinical complications are common in patients with COVID-19 infection, serious adverse events are possible in this setting. Hence, we will establish periodic interim safety review meetings by an independent committee (see also Chapter 1.6).

10.1.1 Definition and assessment of (serious) adverse events and other safety related events

An **Adverse Event (AE)** is any untoward medical occurrence in a patient or a clinical investigation participant administered a pharmaceutical product and which does not necessarily have a causal relationship with the study procedure. An AE can therefore be any unfavourable and unintended sign (including an abnormal laboratory finding), symptom, or disease temporally associated with the use of a medicinal (investigational) product, whether or not related to the medicinal (investigational) product. [ICH E6 1.2]. Any medical conditions present before signing the informed consent will be reported in the medical history. Any AEs that occur between screening and first treatment are considered as Non-Treatment Emergent Adverse Events (TEAE).

A **Serious Adverse Event (SAE)** is classified as any untoward medical occurrence that:

- results in death,
- is life-threatening,
- requires in-patient hospitalization or prolongation of existing hospitalisation,
- results in persistent or significant disability/incapacity, or
- is a congenital anomaly/birth defect.

In addition, important medical events that may not be immediately life-threatening or result in death, or require hospitalisation, but may jeopardise the patient or may require intervention to prevent one of the other outcomes listed above should also usually be considered serious. [ICH E2A]. An elective or pre-planned hospital admission will not be considered as a SAE. Note: an AE or adverse drug reaction is considered 'life-threatening' if, in view of either the Investigator or Sponsor, its occurrence places the patient at immediate risk of death. It does not include an event that, had it occurred in a more severe form, might have caused death.

SAEs should be followed until resolution or stabilisation. Participants with ongoing SAEs at study termination (including safety visit) will be further followed up until recovery or until stabilisation of the disease after termination.

Regardless of the assumed causal relationship, all AE volunteered by the trial subjects or observed by the investigator and/or his staff must be recorded on the AE forms. Records of AEs include patient data, description of the event, intensity, severity, relationship to the study drugs, temporal relation to the study drugs, action taken, description of outcome and documentation of the results of diagnostic and therapeutic measures.

Assessment of Causality

Both Investigator and Sponsor-investigator make a causality assessment of the event to the study drug, based on the criteria listed in the ICH E2A guidelines:

Relationship	Description
Definitely	Temporal relationship Improvement after dechallenge* Recurrence after rechallenge (or other proof of drug cause)

Probably	Temporal relationship Improvement after dechallenge No other cause evident
Possibly	Temporal relationship Other cause possible
Unlikely	Any assessable reaction that does not fulfil the above conditions
Not related	Causal relationship can be ruled out
*Improvement after dechallenge only taken into consideration, if applicable to reaction	

Unexpected Adverse Drug Reaction

An “unexpected” adverse drug reaction is an adverse reaction, the nature or severity of which is not consistent with the applicable product information (e.g. Investigator’s Brochure for drugs that are not yet approved and Product Information for approved drugs, respectively). [ICH E2A]

Suspected Unexpected Serious Adverse Reactions (SUSARs)

The Sponsor-Investigator evaluates any SAE that has been reported regarding seriousness, causality and expectedness. If the event is related to the investigational product and is both serious and unexpected, it is classified as a SUSAR.

Assessment of Severity

The Investigator will be required to assess the intensity of the AE and to record this assessment in the source documents. It is important to distinguish between serious criteria and severity of an AE. Severity is a measure of intensity whereas seriousness is determined by the criteria mentioned above. Investigators will use the following categories to quantify severity.

- Mild/grade 1: events require minimal or no treatment and do not interfere with the patient’s daily activities.
- Moderate/grade 2: events result in a low level of inconvenience or concern with the therapeutic measures. Moderate events may cause some interference with functioning.
- Severe/grade 3: events interrupt a patient’s usual daily activity and may require systemic drug therapy or other treatment. Severe adverse events are usually incapacitating.
- Life threatening/grade 4: potentially life-threatening or disabling. High-risk medical interventions.
- Fatal/grade 5: patient died.

Changes in the severity of an AE will be documented to allow an assessment of the duration of the event at each level of intensity to be performed. AEs characterized as intermittent require documentation of onset and duration of each episode.

10.1.2 Reporting of serious adverse events (SAE) and other safety related events

Reporting of SAEs

The Sponsor-Investigator is responsible for informing all competent authorities (CA) and ethical committees (CEC) of the concerned Member States of any SAEs as per local requirements. Reporting will be performed according to local regulations. This may include the following:

All SAEs must be reported immediately and within a maximum of 24 hours to the Sponsor-Investigator of the study. The Sponsor-Investigator will re-evaluate the SAE and return the form to the site.

SAEs resulting in death are reported to the Ethics Committee (for Swiss sites via BASEC) within 7 days. SAEs resulting in death will be reported to Pharming Technologies, B.V., the manufacturer of the IMP according to the same timelines.

The other in the trial involved Ethics Committees receive SAEs resulting in death in Switzerland via Sponsor-Investigator (for Swiss sites via BASEC) within 7 days.

Reporting of SUSARs

The Sponsor-Investigator will report all SUSARs in compliance with applicable laws and regulations to all Competent Authorities of the concerned Member States (e.g. Swissmedic in Switzerland, AIFA in Italy) and CECs of all study sites (lead EC in Switzerland) within 7 days, if the event is fatal or life-threatening or within 15 days (all other events).

The Sponsor-Investigator must inform all Investigators participating in the clinical study of the occurrence of a SUSAR. All in the trial involved Ethics Committees will be informed about SUSARs in Switzerland via Sponsor-Investigator via BASEC according to the same timelines and according to local regulations in other countries

In addition, the SUSARs will be provided to Pharming Biotechnologies BV, the manufacturer of the IMP, within one business day of submission to the Competent Authorities using a format that is accepted by Pharming Biotechnologies, B.V.

Reporting of Safety Signals

All suspected new risks and relevant new aspects of known adverse reactions that require safety-related measures, i.e. so called safety signals, must be reported to the Sponsor-Investigator within 24 hours. The Sponsor-Investigator must report the safety signals within 7 days to the Ethics Committee (local event via local Investigator) (for Swiss sites via BASEC) and to Swissmedic in case of a category B or C study and according to local regulations in other countries

The Sponsor-Investigator must immediately inform all participating Investigators about all safety signals. The other in the trial involved Ethics Committees will be informed about safety signals in Switzerland via the Sponsor-Investigator and according to local regulations in other countries.

Reporting and Handling of Pregnancies

Pregnancy is an exclusion criteria for the study. Women of childbearing potential must have a negative pregnancy test to be eligible for the study. A pregnancy test will be performed in women who may become pregnant. Pregnant participants must immediately be withdrawn from the clinical study. It is highly unlikely for a pregnancy to occur during the treatment phase. Any pregnancy during the treatment phase of the study and within 30 days after discontinuation of study medication will be reported to the Sponsor-Investigator within 24 hours. The course and outcome of the pregnancy should be followed up carefully, and any abnormal outcome regarding the mother or the child should be documented and reported.

Periodic reporting of safety

The Sponsor Investigator will submit an Annual Safety Report once a year to the CAs and CES of all study sites (lead CEC in Switzerland) or more often if required by local regulations. The Annual Safety Report contains information from all site including information from sites outside of Switzerland. The Sponsor-Investigator prepares the report. In addition, a copy of the report will be sent to Pharming Biotechnologies BV.

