
Measurements and procedures:
	
After providing informed consent a pregnancy test will be performed if appropriate. Only subject who fulfilling all eligibility criteria will be randomised in a 2:1 ratio in an open-label controlled design to treatment with conestat alfa in addition to SOC or SOC only starting on day 0. The first conestat alfa treatment will usually be administered on the same day and continued for a maximum of 64 hours (+/-4 hours).
 
Vital signs, disease severity, clinical improvement, admission to ICU, receipt of additional anti-inflammatory therapies such as tocilizumab and requirement for non-invasive or invasive ventilation will be documented. Disease severity will be evaluated by the WHO Ordinal Scale:
 
  
 Patient State	Description	Score	
   
 Outpatient	No limitation in activities	1	
 
 Limitation in activities	2	
 
 Hospitalized Mild disease	No oxygen therapy	3	
 
 Oxygen by mask or nasal prongs	4	
 
 Hospitalized Severe disease	Non-invasive ventilation or high-flow oxygen	5	
 
 Intubation, mechanical ventilation +/- additional organ support	6	
 
 Death	Death	7	
  
 
Virological clearance will be assessed at 14 days after enrolment or discharge. Routine laboratory parameters and changes in certain biomarker levels will be assessed during 14 days or until discharge.
 
C1INH pharmacokinetics and complement and inflammatory proteins will be assessed (in Basel, optional for other centers) during 14 days or until discharge.
 
Follow-up will include a structured telephone interview or study visit (if still admitted) after 4 weeks to assess adverse events and outcome.
	Patient State	Description	Score	Outpatient	No limitation in activities	1	Limitation in activities	2	Hospitalized Mild disease	No oxygen therapy	3	Oxygen by mask or nasal prongs	4	Hospitalized Severe disease	Non-invasive ventilation or high-flow oxygen	5	Intubation, mechanical ventilation +/- additional organ support	6	Death	Death	7
Patient State	Description	Score																				
Outpatient	No limitation in activities	1																				

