3.3 Preclinical Evidence

The inhibitory potency of conestat alfa towards the target proteases C1s, kallikrein, factor XIa and factor XIIa was found to be comparable with the inhibitory potency of plasma-derived C1-INH, tested *in vitro*. In addition, although C1-INH can inhibit plasmin, tPA and thrombin, inhibition is weak. The expected increases of C1-INH plasma concentrations in the proposed clinical study do not have a significant effect on the activity of the proteases and are unlikely to affect the balance between clotting and fibrinolysis. Please refer to the IB for further information.

In the nonclinical program no concerns were found with respect to tolerability, cardio-respiratory safety, embryofetal toxicity, local tolerance, or immunogenicity of conestat alfa.

Acute and repeat dose toxicology and safety pharmacology as well as local tolerance studies in rats, dogs and rabbits support the safety-in-use of the conestat alfa preparation.

The acute studies showed no overt toxicological effects in rats and dogs with a single dose up to 1250 U/kg. A No-Observed-Adverse-Effect-Level (NOAEL) was established at 625 U/kg when dosed by continuous IV infusions for 14 days in rats and by daily IV infusions (5 mL/min) for 5 days in dogs. In the 14-day pivotal repeat dose toxicity study in monkeys, the NOAEL was established at twice daily IV infusions of 1000 U/kg.

The total dose of 2000 U/kg/day in this monkey study given for 14 consecutive days, exceeds the intended total clinical doses of 150-300 U/kg given a day by 7 to 13-fold without adverse effects.

In a safety pharmacology study in dogs (dosed at 625 U/kg, i.e. 12.5- to 4-fold the intended total clinical dose of 50-150 U/kg), no overt effects on vital functions such as the cardiovascular or respiratory system were observed. The established NOAEL was 625 U/kg.

Conestat alfa is predominantly cleared from the circulation by liver receptors. It is more rapidly cleared from the circulation in rats, dogs and cynomolgus monkeys in comparison with plasma-derived C1-INH. This faster clearance likely results from the differential glycosylation, including a lower degree of sialylation in conestat alfa. Degradation is expected to be by proteolysis/hydrolysis within intracellular lysosomes. From studies in rats, dogs, and cynomolgus monkeys, it can be concluded that conestat alfa distribution is limited to the vascular compartment. For further information, see the IB.

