8.6 Trial specific preventive measures

All participants will receive standard supportive care established at the sites which may include off-label use of certain drugs that are deemed to be effective in COVID-19 (e.g. hydroxychloroquine,

lopinavir/ritonavir). In addition, escalation of treatment with off-label use of certain drugs (e.g. tocilizumab) in deteriorating participants is allowed during the trial. In terms of risk, conestat alfa, a recombinant human protein, has a very favourable side effect profile and major adverse events attributable to study medication are not expected in this study. Anaphylactic reactions are exceptionally rare and have only been observed in a single patient with a pre-existent allergy to rabbits. Although patients with rabbit allergy will be excluded from participating in the study, included subjects will be monitored for anaphylactic events during and at least for at least 12 hours after the last administration of conestat alfa. If patients develop type 1 allergic reactions following the administration of conestat alfa treatment according to in-house guidelines (potentially involving administration of antihistamines, corticosteroids, intravenous fluids and if needed adrenaline) will be provided.

No influence of conestat alfa on laboratory parameters or vital signs, including ECG was observed in previous clinical studies. Hence, we will not perform additional laboratory monitoring exceeding routine laboratory controls planned by the treating team (with the exception of the above mentioned additional biomarker analyses). No interactions with other drugs are known.

If female, patients must be/have: Post-menopausal, defined as the absence of menses for at least one year, OR Surgically sterile, defined as a bilateral tubal ligation at least 6 months prior to administration of study drug, bilateral oophorectomy, or complete hysterectomy, OR using an effective means of contraception with a failure rate less than 1% per year (e.g. oral contraceptives, contraceptive injections, intrauterine device, double-barrier method, male partner sterilization) OR a negative pregnancy test before study entry/randomisation. We expect the rate of female patients of childbearing age who may become pregnant to be <10% of all patients potentially eligible for this study. Due to the short treatment period (3 days) and half-life of conestat alfa (2.5 hours) an effective means of contraception is not mandatory after/during the treatment phase.

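### The protocol gives three different pregnancy-test rules, and two of them let fertile women enter untested although Section 10.1.2 makes a negative test a condition of eligibility

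*Protocol*

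**What the plan says.** The rule appears in several places in protocol version 3.0.

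- **Section 10.1.2** (handling of pregnancies): "Women of childbearing potential must have a negative pregnancy test to be eligible for the study". It continues: "A pregnancy test will be performed in women who may become pregnant". No exemption is given.
- **Study Schedule (front of the protocol), footnote 6:** the same instruction to test women who may become pregnant, without restriction.
- **Section 8.6:** female patients must meet one of four conditions joined by OR. They are post-menopausal status, surgical sterility, "using an effective means of contraception with a failure rate less than 1% per year", or the last item: "OR a negative pregnancy test before study entry/randomisation". The section also expects "the rate of female patients of childbearing age who may become pregnant to be <10% of all patients potentially eligible".
- **Section 9.1 flow chart, footnote 6:** a narrower version of the Study Schedule footnote. It tests only women who could conceive, are sexually active and use no adequate contraception.
- **Section 7.1:** excludes pregnant and breast-feeding women but gives no testing rule.
- **Section 9.3.1, Visit 1:** "Pregnancy test if applicable".
- **Synopsis, Measurements and procedures:** "After providing informed consent a pregnancy test will be performed if appropriate".

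**The concern.** A negative test cannot be a condition of eligibility for every woman of childbearing potential while two other sections describe such women entering without one. The three rules differ in whom they test, and the visit descriptions refer to a rule that is not settled anywhere else.

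At stake is the check behind a safety exclusion, in a trial planned across several centres in Switzerland, Brazil and Mexico. Whether a given woman is tested depends on which page the site reads. A woman enrolled correctly under 8.6 or 9.1 would be an eligibility breach under 10.1.2. That matters within the protocol too: major eligibility violations remove a patient from the per-protocol population (11.4.1), so monitors need a single rule to judge against.

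**Working it through.** **Step 1. Compare the rules on two test cases.**

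| Fertile woman who is… | 10.1.2 | Study Schedule, footnote 6 | 8.6 | 9.1, footnote 6 |
|---|---|---|---|---|
| taking oral contraceptives | test | test | no test needed | no test |
| not sexually active, no contraception | test | test | test | no test |

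The first case sets 10.1.2 and the Study Schedule against 8.6 and 9.1. In the second, 9.1 stands alone against the other three, so 8.6 and 9.1 also disagree with each other. The two copies of footnote 6 contradict each other.

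**Step 2. Look for a reconciling definition.** The texts would agree if contraceptive users and sexually inactive women did not count as being of childbearing potential. The protocol never says so. Footnote 6 in 9.1 lists the ability to become pregnant as a condition separate from sexual activity and contraception, and 8.6 lists contraception separately from post-menopausal and sterile status. A further gap is that 9.1 leaves *adequate* contraception without a failure rate, whereas 8.6 sets one.

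**Step 3. Size of the group.** Inputs: fewer than 10% of eligible patients (8.6), and 120 participants randomised 2:1, that is 80 and 40 (11.2). It is assumed that enrolled patients resemble eligible patients.

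- Fertile women in the trial: <10% × 120 = fewer than 12.
- On conestat alfa: <10% × 80 = fewer than 8.

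These are ceilings for all fertile women. The documents do not say what share would be exempted. If the share is 25% to 75% (assumption):

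- untested in total: 0.25 × 12 = 3 to 0.75 × 12 = 9, so fewer than 3 to 9;
- untested on conestat alfa: 0.25 × 8 = 2 to 0.75 × 8 = 6, so fewer than 2 to 6.

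**Step 4. Undetected pregnancies among women exempted by 8.6.** Inputs: a contraceptive failure rate of 1% per year (the upper limit in 8.6) and a pregnancy going unrecognised for 4 to 12 weeks (assumption).

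- Per woman: 1% × 4/52 = 0.077% to 1% × 12/52 = 0.23%.
- Whole trial, counting all 12 women as exempt to stay on the high side: 12 × 0.077% = 0.009 to 12 × 0.23% = 0.028.
- Active arm, same convention: 8 × 0.077% = 0.006 to 8 × 0.23% = 0.018.
- Cruder figure using a full year of failure: 12 × 1% = 0.12 in the trial and 8 × 1% = 0.08 in the active arm.

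This calculation does not cover women exempted only by 9.1, for whom no failure rate is stated and sexual activity is self-reported.

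**The case against.** The strongest reply is that the protocol can be followed as a whole. Testing every fertile woman satisfies every section: 8.6 and 9.1 forbid no test, and 10.1.2 is the only place that makes the test mandatory for eligibility. On this reading 8.6 is a minimum condition on reproductive status, and a woman on contraception meets it and is still tested under 10.1.2. The risk is also low: known pregnancy always excludes, treatment lasts about three days with a half-life of 2.5 hours, and Section 3.3 states that "no concerns were found with respect to tolerability, cardio-respiratory safety, embryofetal toxicity" in the nonclinical programme. Finally, the exempt share and the recognition window in the sizing are assumptions.

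Much of this stands. One course of action does comply with every section, the conflict in 8.6 is softer than that in 9.1, the risk is low, and beyond the ceilings of 12 and 8 the figures depend on assumed inputs. The contradiction remains, however. Section 8.6 offers the test as one of four alternatives, so its natural reading is that contraception suffices. Footnote 6 in 9.1 states who is tested, and no reading brings it into line with 10.1.2. A site working from the flow chart would not know that it had to test more widely.

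**Conclusion.** The concern holds. The current text states three incompatible testing rules, and two of them allow less than the eligibility condition in 10.1.2. A site acting in good faith could randomise and treat an ineligible woman.

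The scale is small: fewer than 12 fertile women in the trial and fewer than 8 on conestat alfa, if enrolment matches the expectation in 8.6, with only some of them exempted. Under the assumed 4 to 12 week window, expected undetected pregnancies in the group exempted by 8.6 are about 0.01 to 0.03 in the trial and about 0.006 to 0.02 in the active arm. There is no meaningful effect on the statistical analysis. This should be corrected because it concerns a safety exclusion, but it does not threaten the trial's conclusions.

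**What to change.** Apply the 10.1.2 rule throughout: a negative pregnancy test before randomisation in every woman who is neither post-menopausal nor surgically sterile, as 8.6 already defines those terms.

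1. In 8.6, delete contraception as an alternative to the test.
2. In 9.1, replace footnote 6 with the wording of footnote 6 in the Study Schedule.

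It would also help, though it is not essential, to state the test requirement in 7.1, where sites look for eligibility rules. The phrases in the synopsis and 9.3.1 would then refer to a single rule.

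The cost is two wording edits and fewer than 12 additional serum tests. The test is already scheduled at Visit 1, with a 5 ml blood volume allowed for.
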